2.6 Analysis of the key secondary objective

2.6.1 Key secondary endpoint

The key secondary efficacy endpoint of this study is the proportion of subjects with a PASI 90 response at Week 12.

[figure not shown]
2.6.2 Statistical hypothesis, model, and method of analysis

These data will be analyzed in the same way as the primary endpoint though a Bayesian framework.

Efficacy of AIN457 low and high dose compared to historical placebo data will be performed separately. Analyses will be based on the FAS population, and historical placebo data will be incorporation into the analysis as before through the MAP framework.

2.6.3 Handling of missing values/censoring/discontinuations

Missing data will be handled with the same methods as primary endpoint analysis. The bayesian analysis will use pure non-responder imputation and no sensitivity analysis will be performed. Multiple imputation will be used as a sensitivity analysis for the descriptive summary of key secondary endpoints.

2.8 Safety analyses

All safety analyses will be based on the safety set. Only those visits which were pre-planned in the protocol will be reported in tables and figures for safety variables.

The summaries of evaluation will be reported for the entire treatment period, and where appropriate on the entire study period as well.

Data will be presented by the following treatment groups:

- AIN457 low dose: all subjects who were randomized to AIN457 low dose
- AIN457 high dose: all subjects who were randomized to AIN457 high dose
- Any AIN457 dose: data on AIN457 groups above pooled together

Safety analyses will be performed on treatment received or actual treatment (See Section 2.2, Safety Set).

In general, the following guidelines are proposed for safety analysis unless stated otherwise:

- Adverse events: Only treatment emergent records are reported in the tables, and listings have the “treatment emergent” flag displayed.
- Laboratory data (including vital sign and ECG):
 - by period summary statistics tables: only include “on-treatment” records in the tables, i.e., Assessments within last dose plus 84 days cutoff. Listings have the “on-treatment” flag displayed.
 - by visit summary statistics tables: present all “on-treatment” visits, follow up visits (CRF visits) may be summarized separately if required.

In addition to the treatment emergent/on-treatment safety summary, extended entire treatment/study period safety analysis will be provided for AE records up to EOS and for LABs by visit summary statistics up to EOS.

Additional listing will be provided for AE that started after last dose + 84 days through to EOS.

Entire treatment/study period

Entire treatment period = randomization to Week 208 (EOT); for safety analysis include FU period up to last dose + 84 days for early discontinued subjects.

Entire study period = randomization to end of study (EOS); includes follow up period (Week 212, 216 and 224)

For evaluation of entire treatment/study period, AIN457 treatment groups will be pooled to “any AIN457”.

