### **5.5.4 Instructions for prescribing and taking study treatment**

All study treatments will be administered subcutaneously throughout the study. All doses of study treatments at scheduled site visits will be administered at the study site after the study assessments for the visit have been completed. Prior to administration to the subject, the study treatment will be dispensed by the qualified site personnel appointed at the study site.

For home administrations the processes described earlier at [Section 5.5.2](#) must be followed.

The first study treatment administration will occur at the Randomization Visit (Day 1), after all study scheduled assessments have been performed (and inclusion/exclusion criteria confirmed) and only after the scheduled blood samples have been drawn. Similarly, at each other visit, all study assessments should be completed prior to the administration of study treatment.

Subjects will be administered study medication weekly for the first 4 weeks of the treatment period and then every 4 weeks until Week 204.

During the Follow-up period, no study medication will be administered.

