1.1 Study design

This is an open-label, parallel-group, two-arm, multi-center trial in pediatric subjects aged 6 years to less than 18 years with moderate to severe chronic plaque psoriasis.

Approximately 80 subjects (at least 60 patients with moderate severity) will be enrolled. It is expected that subjects will be enrolled in about 40 centers worldwide. It will be targeted to have at least 5 subjects in the < 25 kg weight, and at least 10 subjects in each of the other two weight groups (25 - <50 kg and \geq 50 kg). Subjects will receive the appropriate dose based on their body weight category. If a subject moves into a higher or lower weight group at two consecutive visits with weight measurements from Week 12 onwards, the subject will receive dosing according to the new (higher or lower) weight group respectively. The dose will be adapted starting from the visit of the second consecutive weight change.

The following study periods will be considered for analysis:

Screening Period

The screening period of up to 4 weeks will be used to assess eligibility of the subjects and to taper subjects off prohibited medication.

Treatment Period

The treatment period is defined as randomization to Week 208. In this period the endpoints are assessed and subjects are followed for long-term safety and efficacy. For safety analysis this is defined a last dose + 84 days exposure.

Follow-up Period

The treatment-free follow-up visits will be at Week 212, Week 216 and Week 224 (End Of Follow-up/EOF). Subjects who complete or discontinue treatment early are expected to perform the complete treatment-free follow-up period unless they start another systemic antipsoriatic treatment.

Of note: data from follow-up period for prematurely discontinued subjects will be included in the analysis of treatment period if appropriate.

Entire study period (Randomization to end of study (EOS)), including follow-up period (W212, W216 and W224 visits).

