2.8.1 Adverse events (AEs)

Only treatment emergent adverse events are summarized. However all AEs are included in the listing with flags for treatment emergent. Non-treatment emergent adverse events may be summarized separately upon request.

Treatment emergent adverse events are defined as events started on or after the first dose of study medication or events present prior to the first dose of study medication but increased in severity on or after dosing based on preferred term and within last dose + 84 days (inclusive).

The crude incidence of treatment emergent adverse events will be summarized by primary system organ class and preferred term. Confidence intervals for the crude rate will be derived as described in Section 5 Appendix. In addition, exposure time-adjusted rates (incidence rate) including 95% confidence intervals may be provided, see also Table 2-10.

Table 2-10 Overview of analyses on some safety endpoints

Analysis period	AEs & SPP/RMP risks (special AE interest)	SAEs	AEs-SMQ	AEs by severity	study treatment related AEs, death & other significant AEs	notables (lab/vitals)
initial (Day 1 - week 16)	• crude incidence	• crude incidence	• crude incidence	• crude incidence	• crude incidence	• crude incidence
Entire treatment period	• crude incidence • exp.time adjusted incidence	• crude incidence • exp.time adjusted incidence*	• crude incidence			
Entire study	• exp. time adjusted Incidence*	• exp. time adjusted Incidence*				

*Extended safety summary will be provided for pediatrics trials with FU of 16 weeks

* Please note that exposure adjusted incidence rates may be provided and follow the guideline as below:

- Primary SOC level for AE and SAE
- Level 1 for risks and SMQ
- PT level for SAE
- PT level for AE $\geq 2\%$ or incidence rate per 100 subject years ≥ 5.0 in AIN457 low dose or AIN457 high dose treatment group (may be updated following review of dry run outputs).
- Other selected AEs of special interest on lower levels (e.g. PT or SMQ level 2), if appropriate

The crude incidence of treatment emergent adverse events will be summarized by primary System Organ Class (SOC) and Preferred Term (PT). Confidence intervals for the crude rate will be derived using the score method including continuity correction ([Newcombe 1998](#)) as described in Section 5.4.2. In addition, exposure time-adjusted incidence rates may be provided for the treatment period including all data (see Section 5.4.5).

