Adverse events will be summarized by presenting, for each treatment group (including any AIN457), the number and percentage of subjects having any AE, having an AE in each primary system organ class and having each individual AE (preferred term). The relative frequencies and 95% confidence intervals within each system organ class will be presented for adverse event and serious adverse event in a panel graph (for DMC only).

Summaries will also be presented for AEs by severity and for study treatment related AEs. If a particular AE 'severity' is missing, this variable will be listed as missing and treated as missing in summaries. If a subject reported more than one adverse event with the same preferred term, the adverse event with the greatest severity will be presented. If a subject reported more than one adverse event within the same primary system organ class, the subject will be counted only once with the greatest severity at the system organ class level, where applicable.

The crude incidence of treatment emergent AEs may be repeated and presented by age, disease severity strata and by body weight strata subgroups.

The exposure time-adjusted incidence rate of treatment emergent AEs, SAEs and important identified or potential risks (level 1) in entire treatment period will be summarized, where data permits. Data will be reported by SOC and PT and presented by age, disease severity strata and body weight strata. Crude rate will also be evaluated. Summary by body weight and dose group may be evaluated in addition to the above.

Adverse events will also be reported separately by standardized or customized MedDRA queries (SMQ or CMQ/NMQ). The MedDRA version used for reporting the study will be described in a footnote.

The most common adverse events reported ($\geq z\%$ in any group for each preferred term in the SOC-PT table or $\geq z\%$ in any group for each grouping term table) will be presented in descending frequency according to its incidence in total AIN457 group (combining both AIN457 treatment groups) starting from the most common event. Here threshold value z is set to 2 (%) but it may be updated following review of the dry run outputs.

Separate summaries will be provided for study treatment related adverse events, death, serious adverse event, other significant adverse events leading to discontinuation and adverse events leading to dose adjustment or interruption.

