5.4.5 Exposure adjusted incidence rate and related risk estimates

5.4.5.1 Exposure adjusted incidence rate and $100*(1-\alpha)\%$ confidence interval

It will be assumed that for each of n subjects in a clinical trial the time t_j ($j=1, \dots, n$) to the first occurrence of a certain treatment emergent event is observed, or if the event was not experienced, the (censored) time to the end of the observation period or last dose plus 84 days whichever occur earlier. The sequence of first occurrences of an event will be modeled to follow approximately a Poisson process with constant intensity θ . The rate parameter θ will be

estimated as $\lambda=D/T$, where $T = \sum_{j=1}^n t_j$ and D is the number of subjects with at least one event.

Conditionally on T , an exact $100*(1-\alpha)\%$ confidence interval for a Poisson variable with parameter θT and observed value D can be obtained based on (Garwood, 1936), from which an exact $100*(1-\alpha)\%$ confidence interval for D/T will be derived as follows (Sahai, 1993; Ulm, 1990):

Lower confidence limit $L = \frac{0.5c_{\alpha/2,2D}}{T}$ for $D>0$, 0 otherwise,

Upper confidence limit $U = \frac{0.5c_{1-\alpha/2,2D+2}}{T}$

where $c_{\alpha,k}$ is the α th quantile of the Chi-square distribution with k degrees of freedom.

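### SAP 2.8 ends the safety treatment period at Week 208 for completers but at last dose + 84 days for early discontinuers, against SAP 1.1 and 2.8.1; the exposure rules are split too

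*SAP*

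**What the plan says.** References are to the 2023 SAP; the 2020 SAP words these rules the same way.

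**Period for safety events**
- SAP 2.8, entire treatment period: "randomization to Week 208 (EOT); for safety analysis include FU period up to last dose + 84 days for early discontinued subjects".
- SAP 1.1, treatment period: "For safety analysis this is defined a last dose + 84 days exposure". This has no split by completion status. A note in the same section says that "data from follow-up period for prematurely discontinued subjects will be included in the analysis of treatment period if appropriate".
- SAP 2.8.1 counts an event as treatment-emergent if it starts on or after the first dose, or if it was present before and "increased in severity on or after dosing based on preferred term and within last dose + 84 days (inclusive"). This has no split either.
- SAP 2.8.1 applies the named period to the treatment-emergent tables: exposure-adjusted rates of treatment-emergent AEs, "SAEs and important identified or potential risks (level 1) in entire treatment period will be summarized, where data permits". Table 2-10 has a row for the entire treatment period, with crude and exposure-adjusted incidence.

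**Exposure and time at risk**
- SAP 2.1.1.4 takes exposure to the end-of-treatment visit. It brings in last dose + 84 days (or the last follow-up visit, if earlier) only for early discontinuers.
- The text of SAP 2.4.1 runs to the earlier of last dose + 84 days and the last visit, follow-up visits included. The formula below it takes the earlier of an end-of-treatment-period date and last dose + 84 days.
- SAP 5.4.5.1 censors subjects without the event at "the (censored) time to the end of the observation period or last dose plus 84 days whichever occur earlier". It does not say when the observation period ends.

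**Dosing end.** Protocol 5.5.4 gives study drug "weekly for the first 4 weeks of the treatment period and then every 4 weeks until Week 204".

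**The concern.** A programmer building the Table 2-10 row for the entire treatment period has two stopping rules for the same events. A completer's new event at the Week 212 visit is treatment-emergent under 2.8.1 but outside the period under 2.8. The same event, equally long after the last dose, counts in an early discontinuer. Ascertainment after the last dose then depends on whether the subject completed.

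The second issue is the match between numerator and denominator. Because the exposure and censoring rules have their own end dates, events may be counted to one date and person-time to another.

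At stake is the accuracy of the long-term safety tables in a trial that has long-term safety as a stated purpose. With about 40 subjects per arm, one subject is 2.5%. If the common-event table is shown by arm, that is enough to pass its provisional 2% cut.

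**Working it through.** **Inputs.** Last dose at Week 204 (Protocol 5.5.4); scheduled days in SAP Table 2-3; 84-day window (SAP 1.1, 2.8, 2.8.1); about 80 subjects (SAP 3).

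**1. Reproduce the plan's days.** Scheduled day = 7 × week + 1.
- Week 204: 7 × 204 + 1 = 1429
- Week 208: 7 × 208 + 1 = 1457 (Table 2-3: 1457)
- Week 216: 7 × 216 + 1 = 1513 (Table 2-3: 1513)
- Week 224: 7 × 224 + 1 = 1569 (Table 2-3: 1569)

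Protocol Table 14-1 agrees. Week 208 is 672 h = 28 days after the Week 204 dose (1429 + 28 = 1457), and Week 224 is 3360 h = 140 days after it (1429 + 140 = 1569).

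**2. Gap for a completer on schedule.** Last dose + 84 days = 1429 + 84 = Day 1513, the Week 216 visit. Gap = 1513 − 1457 = 56 days, or 8 weeks. It contains the Week 212 visit (Day 1485) and ends on the Week 216 visit. Post-dose ascertainment under 2.8 is 28 days for completers and 84 for early discontinuers.

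**3. End date for a completer under each rule**

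| Rule | End date |
|---|---|
| 2.8, entire treatment period | Day 1457 |
| 1.1, safety treatment period | Day 1513 |
| 2.8.1, treatment-emergent | Day 1513 |
| 2.1.1.4, exposure | Day 1457 |
| 2.4.1 text, exposure | Day 1513 |
| 2.4.1 formula, exposure | Day 1457, if its end-of-treatment date is read as in 2.1.1.4 |
| 5.4.5.1, censoring | Day 1457 or 1513, depending on the undefined observation period |

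**4. Person-time at issue.** Per completer: 1513/1457 = 1.038, or +3.8%. The number of completers is an assumption (years = n × days / 365.25):
- 80 completers: 319.1 against 331.4 patient-years (+12.3)
- 64 completers: +9.8
- 48 completers: +7.4

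**5. Effect on a rate if events and person-time end on different dates.** Assume a constant hazard r per year, first events only, T1 = 1457/365.25 = 3.989 years and T2 = 1513/365.25 = 4.142 years.

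*Events to Week 216, person-time to Week 208.* Reported rate / r = (1 − exp(−r·T2)) / (1 − exp(−r·T1)).
- r = 1 per 100 patient-years: 1.038 reported, +3.8%
- r = 5: 5.173 reported, +3.5%
- r = 20: 20.495 reported, +2.5%

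*Events to Week 208, person-time to Week 216.* The ratio is the reciprocal. For rare events it tends to 1457/1513 = 0.963, or −3.7%.

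The assumed rates only show the scale; they are not in the documents. Both figures apply to completers. Early discontinuers have the 84-day rule throughout, so the effect over all subjects is smaller.

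**The case against.** The best defence is that the treatment-emergent definition governs. SAP 2.8 says that only treatment-emergent records enter the AE tables, and 2.8.1 sets that window at last dose + 84 days for everyone. Little would be lost in any case. Every AE is listed with a treatment-emergent flag, SAP 2.8 extends the AE analysis to end of study, and Table 2-10 has an entire-study row. Both arms follow the same rule, and the entire-period evaluation pools them, so no dose comparison is biased by design.

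Much of this stands, and it limits the size of the problem. It does not settle the wording. The SAP gives no order of precedence, and 2.8 states an explicit and different safety rule for the named period. The entire-study row shows exposure-adjusted incidence only, with no crude incidence. The extra AE listing starts only after last dose + 84 days, so a completer's events between Weeks 208 and 216 would be in neither that listing nor the treatment-period tables under 2.8. The note in 1.1 on follow-up data for early discontinuers is conditional and sits beside an unqualified safety definition, so it does not resolve the conflict.

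A reader might infer three stronger points that the documents do not support.
- *That completers' person-time after Week 208 is certainly in the 5.4.5.1 denominator.* The rule takes the earlier of two dates, and one is undefined. If the observation period ends at Week 208, 5.4.5.1 agrees with 2.8.
- *That exposure-adjusted rates are therefore lowered.* This depends on the previous point. With exposure ended as in 2.1.1.4 and events counted as in 2.8.1, rates would rise.
- *That a sizeable number of AEs is in or out of the tables.* With an assumed 56 to 72 completers, 56/365.25 years each and 100 to 300 AEs per 100 subject-years, one gets about 9 to 33 events. But the tables count subjects, and 5.4.5.1 counts first occurrences. A term already recorded for a subject over four years adds nothing, so that figure is not the number affected.

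**Conclusion.** The inconsistency is real. SAP 2.8 treats completers and early discontinuers differently after the last dose, while 1.1 and 2.8.1 do not, and the same AE tables use both rules. That conflict does not depend on 5.4.5.1. The exposure and censoring rules add a possible mismatch between events and person-time.

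The effect is small. The gap is 56 days per completer on schedule. Where events and person-time end on different dates, completers' rates for rare events are off by about 3.8% upward or 3.7% downward, and by less for common events. The documents do not fix the direction. These figures assume visits on schedule, a constant hazard and first-event counting.

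The issue is confined to the final descriptive safety tables. The Week 12 co-primary and key secondary analyses are untouched, and the events remain visible in the flagged listing and the entire-study analysis. This is a low-severity point, worth correcting because it is cheap to do so.

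**What to change.** Use one end date for events and person-time, the same for completers and early discontinuers.

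- **SAP 2.8:** define the entire treatment period for safety as first dose to the earlier of last dose + 84 days (inclusive) and last visit, for all subjects. Delete the restriction to early discontinued subjects.
- **SAP 2.1.1.4 and the 2.4.1 formula:** use the same end date for exposure, so that both agree with the 2.4.1 text.
- **SAP 5.4.5.1:** define the end of the observation period as the last visit for this analysis.
- **SAP 1.1:** bring the note on follow-up data for prematurely discontinued subjects into line.

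Changing 2.8 alone would not be enough. Completers' events would then run to Week 216 while their exposure could still stop at Week 208.

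The cost is a few sentences of SAP text and some reprogramming, with no new data, since the follow-up visits are already scheduled for all subjects. The downside is that a few more subjects with AEs are counted and person-time is slightly longer in the treatment-period tables.

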2.8.1 Adverse events (AEs)

Only treatment emergent adverse events are summarized. However all AEs are included in the listing with flags for treatment emergent. Non-treatment emergent adverse events may be summarized separately upon request.

Treatment emergent adverse events are defined as events started on or after the first dose of study medication or events present prior to the first dose of study medication but increased in severity on or after dosing based on preferred term and within last dose + 84 days (inclusive).

The crude incidence of treatment emergent adverse events will be summarized by primary system organ class and preferred term. Confidence intervals for the crude rate will be derived as described in Section 5 Appendix. In addition, exposure time-adjusted rates (incidence rate) including 95% confidence intervals may be provided, see also Table 2-10.

Table 2-10 Overview of analyses on some safety endpoints

Analysis period	AEs & SPP/RMP risks (special AE interest)	SAEs	AEs-SMQ	AEs by severity	study treatment related AEs, death & other significant AEs	notables (lab/vitals)
initial (Day 1 - week 16)	• crude incidence	• crude incidence	• crude incidence	• crude incidence	• crude incidence	• crude incidence
Entire treatment period	• crude incidence • exp.time adjusted incidence	• crude incidence • exp.time adjusted incidence*	• crude incidence			
Entire study	• exp. time adjusted Incidence*	• exp. time adjusted Incidence*				

*Extended safety summary will be provided for pediatrics trials with FU of 16 weeks

* Please note that exposure adjusted incidence rates may be provided and follow the guideline as below:

- Primary SOC level for AE and SAE
- Level 1 for risks and SMQ
- PT level for SAE
- PT level for AE $\geq 2\%$ or incidence rate per 100 subject years ≥ 5.0 in AIN457 low dose or AIN457 high dose treatment group (may be updated following review of dry run outputs).
- Other selected AEs of special interest on lower levels (e.g. PT or SMQ level 2), if appropriate

The crude incidence of treatment emergent adverse events will be summarized by primary System Organ Class (SOC) and Preferred Term (PT). Confidence intervals for the crude rate will be derived using the score method including continuity correction ([Newcombe 1998](#)) as described in Section 5.4.2. In addition, exposure time-adjusted incidence rates may be provided for the treatment period including all data (see Section 5.4.5).

Adverse events will be summarized by presenting, for each treatment group (including any AIN457), the number and percentage of subjects having any AE, having an AE in each primary system organ class and having each individual AE (preferred term). The relative frequencies and 95% confidence intervals within each system organ class will be presented for adverse event and serious adverse event in a panel graph (for DMC only).

Summaries will also be presented for AEs by severity and for study treatment related AEs. If a particular AE 'severity' is missing, this variable will be listed as missing and treated as missing in summaries. If a subject reported more than one adverse event with the same preferred term, the adverse event with the greatest severity will be presented. If a subject reported more than one adverse event within the same primary system organ class, the subject will be counted only once with the greatest severity at the system organ class level, where applicable.

The crude incidence of treatment emergent AEs may be repeated and presented by age, disease severity strata and by body weight strata subgroups.

The exposure time-adjusted incidence rate of treatment emergent AEs, SAEs and important identified or potential risks (level 1) in entire treatment period will be summarized, where data permits. Data will be reported by SOC and PT and presented by age, disease severity strata and body weight strata. Crude rate will also be evaluated. Summary by body weight and dose group may be evaluated in addition to the above.

Adverse events will also be reported separately by standardized or customized MedDRA queries (SMQ or CMQ/NMQ). The MedDRA version used for reporting the study will be described in a footnote.

The most common adverse events reported ($\geq z\%$ in any group for each preferred term in the SOC-PT table or $\geq z\%$ in any group for each grouping term table) will be presented in descending frequency according to its incidence in total AIN457 group (combining both AIN457 treatment groups) starting from the most common event. Here threshold value z is set to 2 (%) but it may be updated following review of the dry run outputs.

Separate summaries will be provided for study treatment related adverse events, death, serious adverse event, other significant adverse events leading to discontinuation and adverse events leading to dose adjustment or interruption.

If for a same subject, several consecutive AEs (irrespective of study treatment causality, seriousness and severity) occurred with the same SOC and PT:

- a single occurrence will be counted if there is ≤ 1 day gap between the end date of the preceding AE and the start date of the consecutive AE
- more than one occurrence will be counted if there is > 1 day gap between the end date of the preceding AE and the start date of the consecutive AE

For occurrence, the presence of at least one SAE / SAE suspected to be related to study treatment / non SAE will be to be checked in a block e.g., among AE's in a ≤ 1 day gap block, if at least one SAE is occurring, then one occurrence is calculated for that SAE.

Algorithms for date imputations will be provided in Section 5 Appendix.

For SAEs occurred during screening a listing will be prepared for all subjects screened including screening failures.

For those subjects who received erroneously the wrong treatment at least once, an additional listing will be prepared displaying all adverse events for that subject and flag AEs that occurred after the first treatment error.

To meet the requirements for posting results to ClinicalTrials.gov and EudraCT, two further tables are produced and final reporting. Treatment emergent adverse events which are not serious adverse events with an incidence greater than X% and a summary for treatment emergent serious adverse events and SAE suspected to be related to study treatment. Summaries are presented by system organ class and preferred term on the safety set population. Here, the threshold value X is set to 2-5 (%) and may be updated following review of the dry run outputs.

Other safety topics of interest, such as risks defined in the Safety Profiling Plan, Risk Management Plan or topics of interest regarding signal detection or routine analysis are defined in the Program Case Retrieval Sheet.

Crude rate of important identified and potential risks from Case Retrieval Sheet will be provided for all (non-serious and serious) cases and for all serious cases. Exposure-time adjusted rates will be provided for treatment period including all data for all (non-serious and serious) cases and for all serious cases. In addition, listings will be provided for the related AE risks.

Risk measures and confidence intervals will be derived according to Section 5.

The version of the Case Retrieval Sheet used for the analyses will be described in a footnote. This includes MedDRA version and Novartis MedDRA Query (NMQ) dictionary date.

Important note: For the evaluation of risks primary and secondary system organ classes of the MedDRA dictionary will be considered.

